8.2.2 Unscheduled Visits

If clinical considerations require the subject to be contacted or seen prior to the next schedule assessment to assure the subject's well-being, it is permissible in this protocol. However, no research data is collected at this visit.

8.3 Adverse Events and Serious Adverse Events

8.3.1 Definition of Adverse Event (AE)

AE means any untoward medical occurrence associated with the use of an intervention in humans, whether or not considered intervention-related. An AE can therefore be any unfavorable and unintended sign (including an abnormal laboratory finding), symptom, or disease temporally associated with the use of medicinal (investigational) product.

Any medical condition that is present at the time that the subject is screened will be considered as baseline and not reported as an AE. However, if the severity of any pre-existing medical condition increases to severity level 3 or 4, it should be recorded as an AE.

Given the nature of severity of the underlying illness, subjects will have many symptoms and abnormalities in vital signs and laboratory values. All Grade 3 and 4 AEs will be captured as

AEs in this trial. In addition, any Grade 2 or higher, suspected drug-related hypersensitivity reaction will be reported as an AE in this trial (see Section 7.1.1).

8.3.2 Definition of Serious Adverse Event (SAE)

An AE or suspected adverse reaction is considered serious (i.e., is an SAE) if, in the view of either the investigator or the Sponsor, it results in any of the following outcomes:

- Death;
- A life-threatening AE;
- Inpatient hospitalization or prolongation of existing hospitalization;
- A persistent or significant incapacity or substantial disruption of the ability to conduct normal life functions; or
- A congenital anomaly/birth defect.

Important medical events that may not meet the above criteria may be considered serious when, based upon appropriate medical judgment, they may jeopardize the subject and may require medical or surgical intervention to prevent one of the outcomes listed in this definition. Examples of such medical events include allergic bronchospasm requiring intensive treatment in an emergency room or at home, blood dyscrasias, convulsions that do not result in inpatient hospitalization, or the development of drug dependency or drug abuse.

“Life-threatening” refers to an AE that at occurrence represents an immediate risk of death to a subject. An event that may cause death if it occurs in a more severe form is not considered life-threatening. Similarly, a hospital admission for an elective procedure is not considered a SAE.

All SAEs, as with any AE, will be assessed for severity and relationship to study intervention.

All SAEs will be recorded on the SAE CRF.

All SAEs will be followed through resolution or stabilization by a licensed study physician (for IND studies, a physician listed on the Form FDA 1572 as the site PI or Sub-Investigator).

All SAEs will be reviewed and evaluated by DMID and will be sent to the DSMB (for periodic review), and the IRB/IEC.

8.3.3 Suspected Unexpected Serious Adverse Reactions (SUSAR)

A SUSAR is any SAE where a causal relationship with the study product is at least reasonably possible but is not listed in the IIB, Package Insert, and/or Summary of Product Characteristics.

8.3.4 Classification of an Adverse Event

The determination of seriousness, severity, and causality will be made by an on-site investigator who is qualified (licensed) to diagnose AE information, provide a medical evaluation of AEs, and classify AEs based upon medical judgment. This includes but is not limited to physicians, physician assistants, and nurse practitioners.

8.3.4.1 Severity of Adverse Events

All AEs and SAEs will be assessed for severity using the DAIDS Table for Grading the Severity of Adult and Pediatric Adverse Events, version 2.1 (July 2017).

For AEs not included in the Table, the following guidelines will be used to describe severity. In addition, all deaths related to an AE are to be classified as grade 5 according to the DAIDS Table.

- Moderate (Grade 2): Events that are usually alleviated with additional specific therapeutic intervention. The event interferes with usual activities of daily living and causes discomfort, but poses no significant or permanent risk of harm to the research subject.
- Severe (Grade 3): Events that interrupt usual activities of daily living, or significantly affect clinical status, or may require intensive therapeutic intervention. Severe events are usually incapacitating.
- Severe (Grade 4): Events that are potentially life threatening.
- Deaths (Grade 5): All deaths related to an AE are to be classified as grade 5. (per DAIDS Table).

AEs characterized as intermittent require documentation of onset and duration of each episode. The start and stop dates (duration) of each reported AE will be recorded on the appropriate CRF. Changes in the severity of an AE will be documented to allow an assessment of the duration of the event at each level of intensity.

8.3.4.2 Relationship to Study Intervention

For each reported adverse reaction, the PI or designee must assess the relationship of the event to the study product using the following guideline:

- Related – There is a temporal relationship between the study intervention and event, and the AE is known to occur with the study intervention or there is a reasonable possibility that the study intervention caused the AE. Reasonable possibility means that there is evidence to suggest a causal relationship between the study intervention and the AE.
- Not Related – There is not a reasonable possibility that the administration of the study intervention caused the event, there is no temporal relationship between the study intervention and event onset, or an alternate etiology has been established.

8.3.5 Time Period and Frequency for Event Assessment and Follow-Up

For this study, all Grade 3 and 4 AEs, all SAEs occurring from the time the informed consent is signed through the Day 29 visit will be documented, recorded, and reported. In addition, any Grade 2 or higher suspected drug-related hypersensitivity reactions associated with study product infusions will be reported as an AE.

8.3.5.1 Investigators Reporting of AEs

Information on all AEs will be recorded on the appropriate CRF. All clearly related signs, symptoms, and results of diagnostic procedures performed because of an AE should be grouped together and recorded as a single diagnosis. If the AE is a laboratory abnormality that is part of a clinical condition or syndrome, it should be recorded as the syndrome or diagnosis rather than the individual laboratory abnormality. Each AE will also be described in terms of duration (start and stop date), severity, association with the study product, action(s) taken, and outcome.

8.3.6 Serious Adverse Event Reporting

8.3.6.1 Investigators Reporting of SAEs

Any AE that meets a protocol-defined criterion as a SAE must be submitted within 24 hours of site awareness on an SAE form to the DMID Pharmacovigilance Group, at the following address:

DMID Pharmacovigilance Group
Clinical Research Operations and Management Support (CROMS)
[name]
[name]
SAE Hot Line: [name] (US) or [name] (outside US)
SAE [contact] (US) or [name] (outside US)
SAE Email Address: [contact]

Other supporting documentation of the event may be requested by the DMID Pharmacovigilance Group and should be provided as soon as possible. The DMID Medical Monitor will review and assess the SAE for regulatory reporting and potential impact on study subject safety and protocol conduct.

At any time after completion of the study, if the site PI or appropriate sub-investigator becomes aware of an SAE that occurred during the subject's participation in the study, the site PI or appropriate sub-investigator will report the event to the DMID Pharmacovigilance Group.

8.3.6.2 Regulatory Reporting of SAEs

Following notification from the site PI or appropriate sub-investigator, DMID, as the IND Sponsor, will report any SUSAR in an IND safety report to the FDA and will notify all participating site PIs as soon as possible. DMID will report to the FDA any unexpected fatal or life-threatening suspected adverse reaction as soon as possible, but in no case later than 7 calendar days after the Sponsor's initial receipt of the information. If the event is not fatal or life-threatening, the IND safety report will be submitted within 15 calendar days after the Sponsor determines that the information qualifies for reporting as specified in 21 CFR Part 312.32. Relevant follow up information to an IND safety report will be submitted as soon as the information is available. Upon request from the FDA, DMID will submit to the FDA any additional data or information that the agency deems necessary, as soon as possible, but in no case later than 15 calendar days after receiving the request.

SAEs that are not SUSARs will be reported to the FDA at least annually in a summary format which includes all SAEs.

Sites may have additional local reporting requirements (to the IRB and/or national regulatory authority).

8.3.7 Reporting of Pregnancy

Pregnancy is not an AE. However, any pregnancy that occurs during study participation should be reported to the Sponsor on the appropriate CRF. Pregnancy should be followed to outcome.

8.4 Unanticipated Problems

8.4.1 Definition of Unanticipated Problems

An Unanticipated Problem (UP) is any event, incident, experience, or outcome that meets the following criteria:

- Unexpected in terms of nature, severity, or frequency given (a) the research procedures that are described in the protocol-related documents, such as the IRB-approved research protocol and informed consent document; and (b) the characteristics of the subject population being studied;
- Related to participation in the research (meaning there is a reasonable possibility that the incident, experience, or outcome may have been caused by the procedures involved in the research); and
- Suggests that the research places subjects or others at a greater risk of harm (including physical, psychological, economic, or social harm) than was previously known or recognized.

8.4.2 Unanticipated Problem Reporting

To satisfy the requirement for prompt reporting, all UPs will be reported using the following timeline:

- UPs that are SAEs will be reported to the IRB and to the Statistical and Data Coordinating Center (SDCC)/study Sponsor within 24 hours of the investigator becoming aware of the event per the above describe SAE reporting process.
- Any other UP will be reported to the IRB and to the SDCC/study Sponsor within 3 days of the investigator becoming aware of the problem.

9. STATISTICAL CONSIDERATIONS

This study is intended to allow for two types of adaptations: 1) sample size re-estimation and 2) addition of new experimental arm(s). A brief summary is provided here. Details will be described in the statistical analysis plan (SAP).

Sample size re-estimation: The target of 400 recoveries corresponds to a total sample size that depends on the proportion of subjects who recover by Day 29. This proportion will be evaluated on pooled (i.e., blinded) data to evaluate the total sample size required. A preliminary estimate based on a 70% recovery probability is 572 patients.

Addition of new experimental therapies: If additional data become available to add an experimental therapy, the sample size will be updated accordingly. Analyses of newly added arm(s) will be performed comparing concurrently enrolled control subjects. This approach was used in the recent PALM study in patients with Ebola virus disease [Mulangu 2019]. Principles of adding arms and addressing questions of “when, what and how” to add them will be developed to guide the study team in their decision-making and will be outlined in a document on interim monitoring.

9.1 Statistical Hypotheses

The primary null hypothesis being tested is that time-to-recovery does not differ between the experimental and control arms.

A key secondary endpoint is the distribution of the 8-point ordinal scale at Day 15. For this, the parameter of interest is the “common odds ratio,” which quantifies the shift in the severity distribution resulting from treatment. For an efficacious treatment, an odds ratio greater than 1 quantifies an improvement in disease severity; a value of 2 indicates a bigger improvement than a value of 1.25. The null hypothesis to be tested is that the odds of improvement on the ordinal scale is the same for the placebo and experimental treatment arms (i.e., the common odds ratio is 1). It is worth noting that, for large sample sizes, the test based on the proportional odds model is nearly the same as the Wilcoxon rank sum test.

9.2 Sample Size Determination

Primary endpoint: The log-rank test will be used to compare treatment arms with respect to time to recovery. For the log-rank test, the two key determinants of power are the total number of events (i.e., recoveries) E and the treatment-to-control ratio of the rate of recovery, R . The number of events required for power $1 - \beta$ to detect a recovery rate ratio of θ using a two-tailed test at $\alpha=0.05$ is approximately

$$E = \frac{4(1.96 + z_{\beta})^2}{\{\ln(\theta)\}^2},$$

where z_{β} is the $100(1 - \beta)$ th percentile of the standard normal distribution.

For 85% power, approximately 320 recoveries are required to detect a 40% increase in the rate of recovery ($\theta = 1.40$) from remdesivir. A recovery rate ratio of 1.40 is similar to, but slightly higher than the figure of 1.31 reported in Cao, Wang, Wen et al. (2020) for a lopinavir/ritonavir trial that used time to improvement by 2 categories as primary endpoint. A total of 400 recoveries is needed for a recovery ratio of 1.35 with 85% power. Table 4 provides power for various recovery rate ratios.

Table 4 Number of recoveries needed for 85% power assuming a type I error rate of 5% for various recovery ratios.

Recovery ratio (θ)	Number of recoveries needed for 85% power
1.25	723
1.30	523
1.35	400
1.40	318

Key secondary: A sample size can be computed using an (assumed) ordinal scale distribution for the placebo and the odds ratio representing clinical improvement. The odds ratio represents the odds of improvement in the ordinal scale for treatment relative to placebo [Whitehead, 1993]. The sample size to detect a given odds ratio for 1:1 randomization using a 2-tailed test at level α is given by

$$\frac{12(z_{\alpha/2} + z_{\beta})^2}{\lambda^2(1 - \sum_{i=1}^K p_i^3)}$$

where λ is the log odds ratio, p_i is the overall probability (combined over both arms) of being in the i th category of the K ordinal outcomes, and $z_{\alpha/2}$ and z_{β} are the $1 - \alpha/2$ and $1 - \beta$ quantiles of the standard normal distribution.

Table 5 displays five scenarios considered for outcome probabilities in the placebo arm for sample size determination. There is significant uncertainty with these assumptions given the limited data available. Table 5 shows a range of sample sizes for odds ratios ranging from 1.25 to 2.5 for 85% power. For 90% power, increase the sample size by 17%. Table 6 displays the probabilities of being in different categories of the ordinal scale under an odds ratio of 1.75. A total sample size of 396 gives approximately 85% power to detect an odds ratio of 1.75 using a 2-tailed test at level $\alpha = 0.05$. The categories of the 8-point ordinal scale are:

- Death;
- Hospitalized, on invasive mechanical ventilation or ECMO;
- Hospitalized, on non-invasive ventilation or high flow oxygen devices;
- Hospitalized, requiring supplemental oxygen;
- Hospitalized, not requiring supplemental oxygen - requiring ongoing medical care (COVID-19 related or otherwise);
- Hospitalized, not requiring supplemental oxygen - no longer requires ongoing medical care;
- Not hospitalized, limitation on activities and/or requiring home oxygen;
- Not hospitalized, no limitations on activities.

Note that the data elements contributing to this scale will be captured separately, in order to facilitate different orderings or groupings, as might arise if external data provide information about the clinical course of disease.

Table 5. Possible scenarios for the distribution of ordinal outcomes for the control arm at Day 15.

	Anticipated	Different scenarios for control arm			
	Scenario 1	Scenario 2	Scenario 3	Scenario 4	Scenario 5
		more mild disease ← → more severe disease			
Severity Outcome	outcome (%)	outcome (%)	outcome (%)	outcome (%)	outcome (%)
Death	2	1	1	2	3
Hospitalized, on mechanical ventilation or ECMO	1	1	1	1	3
Hospitalized, on non-invasive ventilation or high flow oxygen devices	2	1	1	2	4
Hospitalized, requiring supplemental oxygen	7	2	5	5	9
Hospitalized, not requiring supplemental oxygen - requiring ongoing medical care (COVID-19 related or otherwise)	8	5	7	17	23
Hospitalized, not requiring supplemental oxygen - no longer requires ongoing medical care	10	9	10	20	25
Not hospitalized, limitation on activities and/or requiring home oxygen	30	36	35	25	18
Not hospitalized, no limitations on activities	40	45	40	28	15

Table 6. Sample size calculations for scenarios in Table 5 for a two-arm study assuming 85% power, a two-sided type I error rate of 5%, and various true odds ratios.

True odds ratio	Total sample size				
	Scenario 1	Scenario 2	Scenario 3	Scenario 4	Scenario 5
1.25	2420	2554	2459	2293	2252
1.5	744	786	755	700	684
1.75	396	419	401	370	360
2.0	262	277	265	243	236
2.25	194	206	196	179	173
2.5	154	163	155	141	136

Table 7. Treatment ordinal outcome proportions under an odds ratio of 1.75 for five scenarios in Table 6 at Day 15.

	Scenario 1		Scenario 2		Scenario 3		Scenario 4		Scenario 5	
	Anticipated		more mild disease ←→ more severe disease							
Severity Outcome	Control %	Treatment %	Control %	Treatment %	Control %	Treatment %	Control %	Treatment %	Control %	Treatment %
Death	2	1.2	1	0.6	1	0.6	2	1.2	3	1.7
Hospitalized, on mechanical ventilation or ECMO	1	0.6	1	0.6	1	0.6	1	0.6	3	1.8
Hospitalized, on non-invasive ventilation or high flow oxygen devices	2	1.2	1	0.6	1	0.6	2	1.2	4	2.5
Hospitalized, requiring supplemental oxygen	7	4.3	2	1.2	5	3.0	5	3.1	9	5.8
Hospitalized, not requiring supplemental oxygen - requiring ongoing medical care (COVID-19 related or otherwise)	8	5.3	5	3.1	7	4.4	17	11.5	23	17.4
Hospitalized, not requiring supplemental oxygen - no longer requires ongoing medical care;	10	7.2	9	5.9	10	6.8	20	16.2	25	24.4
Not hospitalized, limitation on activities and/or requiring home oxygen	30	26.5	36	29.3	35	30.2	25	25.9	18	22.7
Not hospitalized, no limitations on activities	40	53.8	45	58.9	40	53.8	28	40.5	15	23.6

Note that columns may not sum to exactly 100 due to rounding errors.

9.3 Populations for Analyses

The primary analysis will be based on an intention-to-treat population, including all subjects randomized. Similarly, safety analyses will be based a modified intent-to-treat population consisting of all subjects who received at least one infusion. The primary analysis will be based on those subjects enrolled in order to 400 recoveries. Subsequent analysis will be performed on all enrolled subjects.

9.4 Statistical Analyses

9.4.1 General Approach

This is a double-blind placebo controlled randomized trial testing a superiority hypothesis with a two-sided type I error rate of 5%. Secondary hypotheses have been ordered according to relative importance, with one key secondary hypothesis highlighted. These will be described according to the appropriate summary statistics (e.g., proportions for categorical data, means with 95% confidence intervals for continuous data, median for time-to-event data).

A statistical analysis plan will be developed and filed with the study sponsor prior to unblinding of study and database lock.

Unblinding of the study will occur after all subjects enrolled for 400 recoveries have reached the end of study, and these visits are monitored and data is cleaned.

9.4.2 Analysis of the Primary Efficacy Endpoint

The primary efficacy analysis is a stratified log-rank test, where stratification is according to baseline disease severity (i.e. protocol defined mild/moderate vs severe disease). Deaths will be considered censored at Day 29.

9.4.3 Analysis of the Secondary Endpoint(s)

- 1) The ordinal scale will be used to estimate a proportional odds model by disease strata. The hypothesis test will perform a stratified test to evaluate whether the common odds ratio for treatment is equal to one. The distribution of severity results will be summarized by treatment arm as percentages. Efforts to minimize loss-to-follow-up will be considerable. However, small amounts of missing data may occur. In such cases, subjects without final outcome data will be excluded from the analysis. Sensitivity analyses will evaluate the impact of making different assumptions about missing observations. These analyses will be defined in the SAP.
- 2) Differences in time-to-event endpoints (e.g., time to at least a one category improvement in ordinal scale) by treatment will be summarized with Kaplan-Meier curves and 95% confidence bounds. The same procedure will be used to compare time to at least a two category improvement.

- 3) Change in ordinal scale at specific time points will be summarized by proportions (e.g., proportion who have a 1-, 2-, 3-, or 4-point improvement or 1-, 2-, 3-, 4-point worsening).
- 4) Duration of event (e.g., duration of mechanical ventilation) will be summarized according to median days with quartiles.
- 5) Binary data (e.g., incidence of new oxygen use) will be summarized as a percent with 95% confidence intervals. Comparisons between arms will be presented as differences in proportions with 95% confidence intervals.
- 6) Categorical data (e.g., 28-day mortality or ordinal scale by day) may be summarized according to proportions by category and/or odds ratios with confidence intervals.

Procedures for handling missing data, including informative censoring (e.g., a missing duration of oxygen use endpoint due to a death), will be described in the SAP.

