3.3.3. Clinical Status At Specific Timepoints

The key secondary analyses include evaluation of the clinical status score at Day 15. For this outcome, Study Visit Day 15 is the timepoint of interest, not necessarily the actual study day. The score collected at the study visit corresponding to Day 15 will be used for this outcome. For analyses of this outcome, imputation of the clinical score may be performed following the rules described in Section 6.5.

Additional analyses are clinical status at Days 3, 5, 8, 11, 15, 22, and 29. As the with above, the scores that will be used are those collected at the study visits corresponding to those days.

Sensitivity analyses of the key secondary outcome will be performed where subjects who were unblinded and crossover treated with remdesivir prior to Day 15 will have their latest CSO score pre-remdesivir treatment carried forward to Day 15. A similar process will be used for the unblinding sensitivity analysis.

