4. INVESTIGATIONAL PLAN

4.1. Overall Study Design and Plan

This study is an adaptive, randomized, double-blind, placebo-controlled trial to evaluate the safety and efficacy of novel therapeutic agents in hospitalized adults diagnosed with COVID-19. The study is a multicenter trial that will be conducted in up to approximately 100 sites globally. The study will compare different investigational therapeutic agents to a control arm. There will be interim monitoring to allow early stopping for futility, efficacy, or safety. If one therapy proves to be efficacious, then this treatment may become the control arm for comparison(s) with new experimental treatment(s). Any such change would be accompanied by an updated sample size. Because background standards of supportive care may evolve/improve over time as more is learned about successful management of COVID-19, comparisons of safety and efficacy will be based on data from concurrently randomized subjects. An independent Data and Safety Monitoring Board (DSMB) will actively monitor interim data to make recommendations about early study closure or changes to study arms.

Recruitment will continue until there are 400 subjects with a “recovered” status (per the primary objective). The primary analysis will be based the total number of subjects enrolled to achieve 400 recoveries. An additional analysis of the moderate severity subgroup (those with baseline status of “Hospitalized, requiring supplemental oxygen” or “Hospitalized, not requiring supplemental oxygen - requiring ongoing medical care”) is also of public health importance. Hence, enrollment will be permitted until the date of April 20, 2020 to ensure 400 recoveries and provide additional data about this important subgroup. With recent enrollment rates, the total sample size may be 600 to over 800.

If any additional therapeutic arms are added, the sample size will be recalculated.

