6.2.3. Final Analyses

After the DSMB meeting on April 27, 2020, the interim results were provided to the sponsor and the interim analyses were performed again on an April 28, 2020 database freeze (unlocked dataset). The results of these analyses were made public on April 29, 2020. Subsequent to this, the plan for the final analyses (and corresponding datasets) was modified to the following:

- A preliminary analysis of the primary, key secondary, and major safety outcomes will be performed on unlocked, partially clean version of data and events that occurred up to April 28, 2020. This preliminary analysis dataset was used for the analyses and summaries included in the “Remdesivir for the Treatment of Covid-19 – Preliminary Report” article published in The New England Journal of Medicine on May 22, 2020 (DOI: 10.1056/NEJMoa2007764) and will be used for the preliminary report, whose summaries will coincide with the summaries provided in the article. This dataset will not be used for any further analyses apart from the preliminary report.
- A fully cleaned and locked version of data and events that occurred up to April 28, 2020 will be denoted as the “early analysis set”. Section 7, Section 8, and Section 9 denote which summaries will be provided as part of this report, but will focus largely on primary outcome, key secondary outcome, and mortality.

- The final analyses of all outcomes and planned summaries/listings will be performed on the final full locked database and provided in an addendum to the final report. This is the fully cleaned and locked version of all data and events that occurred at any time during this trial and will be denoted as the “full analysis dataset”.

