6.5. Missing Data

All attempts will be made to collect all data per protocol. Any data point that appears to be erroneous or inexplicable based on clinical judgment will be investigated as a possible outlier. If data points are identified as outliers, sensitivity analyses may be performed to examine the impact of including or excluding the outliers. Any substantive differences in these analyses will be reported.

For time to event outcomes, subjects who are lost to follow-up or terminate the study prior to Day 29 and prior to observing/experiencing the event will be censored at the time of their last observed assessment. Subjects who die prior to observing/experiencing the event will be censored at Day 29.

For the analysis of the key secondary outcome, subjects who are discharged but are subsequently re-admitted prior to Day 15 without a reported clinical score, their clinical score will be imputed at 7, which is the highest value for a hospitalized subject.

For the analyses of the secondary outcomes that involve clinical score (i.e. the key secondary outcome and time to improvement), if a subject is discharged from the hospital without a previously or concurrently reported clinical score of 1 or 2, then their clinical score at the time of discharge will be imputed as 2, which is the highest value for a non-hospitalized subject.

For the modified version of the ordinal score described in Section 4.3, if a subject is discharged from the hospital without a previously or concurrently reported clinical score of 2 or 3, then their clinical score at the time of discharge will be imputed as 3, which is the highest value for a non-hospitalized subject.

For the analyses of the secondary outcomes described in Section 3.3, the following imputation rules will be used for subjects who are lost to follow-up, terminate early from the study, or do not have further outcome data available after discharge for any reason:

- Days of Non-invasive ventilation/high-flow oxygen:
 - If the subject's clinical status scale is 6 at the last observed assessment, then the subject will be considered to be on non-invasive ventilation/high-flow oxygen

- through Day 29. The endpoint will be total days when assessments are available plus all imputed days following the last observed assessment.

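### The SAP omits the missing-data analyses promised for the Day 15 ordinal outcome, and in the April 28 datasets inclusion of late-enrolled subjects depends on their outcome

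*Protocol*

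**What the plan says.** **Protocol 9.4.3** expects small amounts of missing data on the ordinal scale and sets a complete-case rule: "In such cases, subjects without final outcome data will be excluded from the analysis". It continues: "Sensitivity analyses will evaluate the impact of making different assumptions about missing observations", and "These analyses will be defined in the SAP".

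**SAP 3.3.3** defines the key secondary outcome by visit: "The score collected at the study visit corresponding to Day 15 will be used for this outcome". It adds that scores may be imputed under SAP 6.5.

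**SAP 6.5** has two score rules for this outcome on the 8-point scale. For a subject readmitted before Day 15 without a score, "their clinical score will be imputed at 7, which is the highest value for a hospitalized subject". The second rule applies "if a subject is discharged from the hospital without a previously or concurrently reported clinical score of 1 or 2"; the score at the time of discharge is then set to 2.

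**SAP 6.2.3** lists three datasets. The first is preliminary: "A preliminary analysis of the primary, key secondary, and major safety outcomes will be performed on unlocked, partially clean version of data", with events up to April 28, 2020. The second, the early analysis set, is the cleaned and locked version with the same cut, and its report is to centre on the primary outcome, the key secondary outcome and mortality. The third is the full locked database. SAP 8.2.1 does not itself name the early set, so its use for this endpoint rests on 6.2.3.

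**SAP 4.1** states that "enrollment will be permitted until the date of April 20, 2020". The visit schedule gives Day 15 a window of ±2 days. The Table 34 shell scores a death at or before a visit as 8.

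**The concern.** There are two linked gaps.

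First, the protocol hands the missing-data sensitivity analyses for its key secondary outcome to the SAP, and the SAP does not supply them.

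Second, the complete-case rule was written for occasional loss to follow-up. A cut eight days after the last permitted enrolment produces a different kind of missingness: some subjects have simply not reached Day 15. Among them, a death settles the Day 15 score in advance, while survival leaves it open. Complete-case analysis then keeps the deaths and loses at least the survivors still in hospital. The Day 15 distribution is distorted. The odds ratio also depends on how discharged late subjects are handled, which the SAP leaves unclear. SAP version 3.0 was written after the interim results had been presented, so the choice should be fixed in the text and not left to the analyst.

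**Working it through.** **1. Promise against delivery.** The sensitivity analyses that the SAP defines for the key secondary outcome cover unblinding and crossover (3.3.3, 8.2.1), concomitant therapy (6.4) and a modified scale (4.3, 8.2.1). None varies an assumption about a missing Day 15 score. SAP 6.5 has rules for loss to follow-up for days of oxygen, ventilation and hospitalisation, but none for a subject in hospital or lost without a Day 15 score.

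**2. The plan's own figure.** Both documents give N = 12(z_α/2 + z_β)² / [λ²(1 − Σp_i³)]. For Scenario 1, odds ratio (OR) 1.75, 85% power and two-sided 5%: (1.960 + 1.036)² = 8.978, λ² = 0.5596² = 0.3132, and Σp_i³ = 0.1270 with the arms averaged. N = 107.74 / (0.3132 × 0.8730) = 394, against the stated 396. The scenario inputs are therefore read correctly.

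**3. Calendar** (Day 1 = day of randomisation, so nominal Day 15 = randomisation date + 14).

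| Randomised | Nominal Day 15 | Window ±2 | Visit by April 28? |
|---|---|---|---|
| April 12 | April 26 | April 24-28 | Window closed |
| April 13 | April 27 | April 25-29 | Not assured |
| April 14 | April 28 | April 26-30 | Not assured |
| April 15 | April 29 | April 27-May 1 | Only if early |
| April 16 | April 30 | April 28-May 2 | Only on the cut date |
| April 17 | May 1 | April 29-May 3 | Impossible |
| April 20 | May 4 | May 2-6 | Impossible |

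**4. Size.** Let f be the fraction of subjects without a Day 15 visit by the cut. The documents do not give f, so 5%, 12% and 25% are assumed; 12% would be 6 of 50 days (March 2 to April 20) under even accrual. Other inputs are the Scenario 1 control distribution (2/1/2/7/8/10/30/40%, death to best), OR 1.75, and N = 800 from the stated range of 600 to over 800. The illustration counts every late death by Day 15 as known at the cut, which overstates the inflation of deaths.

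*Reading A: all late survivors dropped.* Control death share = 0.02 / (1 − f + 0.02f):
- f = 5%: 0.02 / 0.951 = 2.10%
- f = 12%: 0.02 / 0.8824 = 2.27%
- f = 25%: 0.02 / 0.755 = 2.65%

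Subjects lost = 400f(0.98 + 0.9885) = 787.4f.

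*Reading B: late subjects discharged by Day 15 kept as score 2.* Only those alive in hospital are lost: 28% of control and 18.5% of treatment, or about 186f. This assumes that all were out by the cut and that none had a recorded 1.

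Fitting the proportional odds model to the expected cell counts gives:

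| f | A: lost of 800 | A: OR | B: lost of 800 | B: OR |
|---|---|---|---|---|
| 5% | 39.4 | 1.751 | 9.3 | 1.720 |
| 12% | 94.5 | 1.752 | 22.3 | 1.680 |
| 25% | 196.8 | 1.755 | 46.5 | 1.616 |

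Under B, late discharged subjects all score 2. The contrast between categories 1 and 2, which carries much of the Scenario 1 effect (40% against 53.8% in category 1), is lost for them. In Scenario 5 the OR stays at 1.75-1.76 under both readings.

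The formula implies a standard error for log OR of √[12 / (800 × 0.873)] = 0.131. The shift under B is ln 1.75 − ln 1.72 = 0.017 up to ln 1.75 − ln 1.616 = 0.080, or about 0.13 to 0.6 standard errors.

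Power at OR 1.75 under A falls from 98.9% to 98.6%, 98.0% and 96.0%. At OR 1.5 it falls from 87.5% to about 77% at f = 25%.

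**5. Type I error.** With no treatment effect, the selection acts alike in both arms. The calculation gives no sign of inflation.

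**The case against.** The strongest reply is that the effect is small and confined. The full locked dataset has no cut problem. The preliminary dataset had already been published and serves only its own report, so a new rule can change only the early analysis set. The Table 34 shell shows subjects without a score in separate rows for hospitalised and discharged subjects, so the missingness is visible. Mortality to Day 15 is analysed as time to event with censoring, so incomplete follow-up is handled there. All of this stands and limits the reach of the point. It does not supply the promised sensitivity analyses or an inclusion rule for the early set.

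A reader might infer three stronger things that the documents do not support:

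- *Everyone randomised after April 14 lacks a score unless dead.* The ±2-day window lets subjects randomised April 15 or 16 have a valid visit by the cut.
- *All late survivors are lost.* SAP 6.5 may keep discharged subjects at score 2. It sets the score at discharge and does not say whether it carries to Day 15, so both readings remain open.
- *The odds ratio is pushed in favour of treatment, or the test is anti-conservative.* Under Reading A the OR barely moves. Under Reading B it moves toward 1 in Scenario 1 and hardly at all in Scenario 5.

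The selective retention of deaths is itself an inference from SAP 6.2.3 and the Table 34 shell. No rule states it, but no rule prevents it.

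**Conclusion.** The point holds in a limited form. The missing-data sensitivity analyses that Protocol 9.4.3 assigns to the SAP are absent; this follows from the text and needs no assumption. In the April 28 datasets, as the plan stands, inclusion in the Day 15 analysis depends on outcome for subjects randomised April 17-20 and for some randomised April 13-16.

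With 5-25% of subjects affected, Scenario 1 and a true OR of 1.75, the control death percentage rises by 0.1 to 0.65 points. The OR is 1.75-1.76 or 1.72-1.62, depending on a handling choice that the SAP does not make. These figures are illustrations: the affected fraction is assumed, and Reading B is an extreme case. The early report risks a distorted Day 15 distribution, a smaller sample and an estimate that depends on an unstated rule. The full-set result is not threatened by the cut. The plan should be amended, but this does not undermine the trial's conclusion.

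**What to change.** (a) In the early analysis set, limit Day 15 analyses to subjects randomised early enough, whatever their outcome. On or before April 14 is the nominal boundary, but it leaves some subjects from April 13-14 whose in-window visit may follow the cut. On or before April 12 ensures that the whole window has closed. Note in the report that the published preliminary analysis had this limitation.

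(b) State whether the discharge score carries to Day 15 when there is no Day 15 contact. Keep a recorded 1 or 2, and use 2 only where neither was reported, so that the rule agrees with SAP 6.5.

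(c) Define the promised sensitivity analyses on the full set, for example multiple imputation from last score, severity and arm, with worst-case and best-case bounds.

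The cost is SAP wording, a few extra runs and a smaller early Day 15 sample.
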